5.7 Withdrawal of Subjects

Participants can be withdrawn from the study by the investigators and study staff if they do not meet all of the inclusion criteria, have more than 4 no-show appointments without excuse, demonstrate non-compliance on study tasks, exhibit excessive frustration and emotional reactions to study procedures that do not subside with re-instruction, discussions about the purpose of the tasks, breaks or rescheduling.

Participants can withdraw at any time without penalty. They can inform an investigator or study staff in person, by telephone or in writing. Participants withdrawn from the study will be informed in person or by telephone by an investigator or study staff. All participants who withdraw or are withdrawn from the study will be supplied with form 10-1016 - Revocations for use and release of IIHI for VHA Research.

All of the participants with hearing impairment will be referred to their local VA for audiological services and follow-up. Participants with PTSD will be referred to their local VA for behavioral health services if they are not receiving services currently.

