- b. Are certain test procedures and stimuli particularly sensitive to the deficits found with this population of veterans and are deficit patterns influenced by the coexistence of PTSD?
- c. Does the addition of background noise produce over-additive effects in this population of veterans and does PTSD increase the effect?
- d. Does this population of veterans perceive and demonstrate benefit when fitted with hearing aids that provide mild high-frequency gain and does PTSD influence benefit?
- e. Is hearing aid benefit predictable by measures of auditory processing, speech perception, psychoacoustic, verbal working memory, and language processing? Furthermore, does the coexistence of PTSD influence the relationship between these measures and hearing aid benefit?

Expected Outcomes

- a. This population of veterans will differ from veterans with no history of blast exposure, and the presence of PTSD will increase severity and alter the deficit pattern.
- b. This population of veterans will experience significant problems with the addition of background noise and the effect will be influenced by linguistic load, verbal working memory and attention.
- c. This population of veterans will demonstrate and perceive benefit from being fitted with mild-gain high-frequency hearing aids, although the coexistence of PTSD will restrict perceived benefit.
- d. Mild-gain high-frequency amplification will improve speech perception skills in quiet and noise, and improve linguistic processing and executive function.
- e. Benefit from amplification will relate to the deficits that the veterans present.

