Interested veterans will first be screened by telephone. For those veterans who pass the screen, the testing (preliminary and experimental) will be conducted across multiple sessions at one of the study sites. The first session will include the preliminary measures such as standard audiometric tests, questionnaires, and a vision screen to ensure appropriate inclusion and exclusion of participants. The subsequent experimental sessions will include additional questionnaires and assessment procedures. It is estimated that the preliminary and experimental testing will require about 8 to 12 hours, with the total time dependent on patient characteristics (e.g., fatigue, response speed, need for breaks, task tolerance). It is anticipated that most participants will be able to complete all of the procedures in Part 1 within 4 to 5 sessions, but 4 additional sessions will be allowed if more time, shorter sessions, or frequent breaks are needed. Our clinical experience with the targeted populations is that 2 to 3 hour sessions are tolerated well and not burdensome. [name] et al. (2011) used a similar battery and test burden was not mentioned as a factor in their publication.

Telephone Screen – After describing the study to prospective veteran participants, those who remain interested in participating will be asked a series of screening questions to ensure that they are within the targeted age range, can read and write well enough to complete the tasks, have no prior history of hearing aid use, have brain injury or disorder within the severity range targeted by the study, and whether they can be paid by direct deposit. Veterans passing the telephone screen and who wear corrective lenses will be asked to bring their glasses or contacts to the subsequent sessions so they will be able to complete forms, the Snellen screen, questionnaires, and other tasks involving visual processing.

Preliminary Tests – Preliminary assessment procedures will be administered to determine group placement and exclude participants who might have difficulty completing the study. The procedures include the following:

- a. A case history that includes questions targeting hearing, tinnitus, blast exposure, concussion, brain injury, PTSD, headache, pain, communication problems, academic histories, employment status and other demographic data (Attached).
- b. Brief Traumatic Brain Injury Screen (BTBIS; Schwab et al., 2006) to determine probable mTBI

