- c. PTSD Checklist-Military Version (PCL-M: National Center for PTSD-Behavioral Division; Weathers et al., 1994) to screen for PTSD
- d. Hearing Handicap Inventory in Adults (HHIA, Newman et al., 1993) to document self-perceived hearing handicap. It will be administered at the beginning and end of Part 1 to document baseline handicap status prior implementing Part 2 of the study.
- e. A standard audiometric hearing test battery that includes otoscopy, tympanometry, and an acoustic reflex screen at 1000 Hz, air- and bone-conduction pure-tone threshold testing (ASHA, 2005), and the Northwestern University Test # 6 (NU-6; Tillman & Carhart, 1966)
- f. Loudness discomfort levels (LDLs) for tones at 500, 1000, 2000 and 4000 Hz according to procedures recommended by Sherlock and Formby (2005) to document hyperacusis
- g. Snellen chart to screen vision

- h. Motor-Free Visual Perception Test, version 4 (MVPT-4) to document that the subjects have the basic visual processing skills to perform tasks that include visual stimuli

Table 1. Group inclusion criteria based on preliminary test measures.

PRELIMINARY ASSESSMENT	GROUPS			
	mTBI-only	mTBI+PTSD	PTSD-only	Normal Controls
Blast Exposure History	Yes	Yes	No	No
Normal or Near Normal Standard Audiometric Test Results	Yes	Yes	Yes	Yes
History of Wearing Hearing Aids Consistently	No	No	No	No
BTI	Evidence of Brain Injury	Evidence of Brain Injury	No Evidence of Brain Injury	No Evidence of Brain Injury
PCL-M	≤ 20	> 20	> 20	≤ 20
HHIE	> 16	> 16	Not considered	≤ 16
LDLs	No Hyperacusis	No Hyperacusis	No Hyperacusis	No Hyperacusis
Snellen (corrected or uncorrected)	20/30	20/30	20/30	20/30
MVPT-4	$> 5^{\text{th}}$ percentile	$> 5^{\text{th}}$ percentile	$> 5^{\text{th}}$ percentile	$> 5^{\text{th}}$ percentile

Experiment Procedures

Part 1 Procedures

The experimental procedures are listed below according to type of assessment. Most are commonly used clinical procedures and will be completed in the standard manner.

Health and Quality of Life Questionnaires –

- a. World Health Organization Disability Assessment Schedule II (WHODAS II) as a measure of general health status and quality of life (McArdle et al., 2005)
- b. Satisfaction with Life Scale (SWLS) to document health-related quality of life
- c. Brief Symptom Inventory-18 Item (BSI-18) to document self-perceived psychiatric and psychological status

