- d. The Speech, Spatial and Qualities of Hearing Scale (SSQ; Gatehouse & Noble, 2004) to assess self-perceived functional and situational auditory skills not covered by the other questionnaires. Like the HHIA, the SSQ will be presented at the beginning and end of Part 1 to establish the pretreatment baseline for Part 2.
- e. The Tinnitus Functional Index (TFI; Meikle et al., 2012) will be administered because many patients with mTBI and PTSD complain of tinnitus and it can impact perceived handicap and quality of life (Fagelson, 2007), although it should be noted that in our chart review of the target population tinnitus was not a primary complaint with only 21.7% reporting any tinnitus.
- f. The Hearing Handicap Inventory for Adults-Significant Other (HHIA-SO; Newman & Weinstein, 1988) will be completed by a significant family member or friend (if available) to capture auditory-related problems noticed by others but not by the participants. The veteran will give the questionnaire to a family member or friend to complete and mail to the study site. These data will be kept confidential from the veteran, and the family members or friends can refuse to participate by not completing or mailing the questionnaire.
- g. HHIA will be repeated to document stability of handicap.
- h. Information about general medical history, blast and head injury, neurological history; audiology assessment history and behavioral health diagnosis and treatment history also will be collected from the VA Computerized Patient Record System (CPRS) to confirm status.

Peripheral Auditory System –

- a. Distortion product otoacoustic emission (DPOAE) to assess cochlear integrity
- b. Fast Psychophysical Tuning Curves (FPTC) to determine filtering and spectral tuning properties of each ear. The fast tuning curves will be obtained for 2000 and 4000 Hz signals using the procedures and software developed by Sek and Moore (2011).
- c. Temporal Fine Structure 1 test (TFS1; Moore & Sek, 2009) to assess the ability of the cochlea to process fine acoustic structures.

Central Auditory System –

- a. Tonal and speech Masking Level Difference (MLD) tests according to procedures described by (Wilson et al, 2003; Wilson et al., 1994).
- b. Competing Sentences subtest from the SCAN-3A to measure the ability to focus on a primary speech signal and ignore background speech
- c. Two-digits section of the Dichotic Digits Test (DDT; Musiek, 1983) to assess dichotic auditory function

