Delayed-Treatment Control Group – The participants in the delayed-treatment control group will be selected from the mTBI-only group and followed over a 12-month period (+/- 2 weeks). At the onset of Part 2 they will complete the HHIA, SSQ, and the unaided portion of the APHAB. They will complete the speech perception and language tasks administered to the treatment group (CCT, phonetic context effect, and CRTT tasks) but unaided only. The delayed-treatment groups will receive home visits at 1, 2, 4 months (+/- 1 week) post-entry, at which times they will complete the HHIA, SSQ, and the unaided portion of the APHAB. At 6 months post-entry their pure tone hearing thresholds will be measured to determine possible changes in hearing sensitivity, and the procedures used with the treatment groups will be applied with the same sequence of follow-up sessions.

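### PTSD is scored once, at Part 1 screening, and that label may be out of date when Part 2 asks whether PTSD influences hearing aid benefit

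*Combined protocol and SAP*

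**What the plan says.** **When PTSD is scored.** In section 5.1 the PCL-M is listed among the Part 1 preliminary tests, "to screen for PTSD". On those tests the section states: "Preliminary assessment procedures will be administered to determine group placement and exclude participants who might have difficulty completing the study". Table 1 separates mTBI-only from mTBI+PTSD at one PCL-M cut (20 or below against above 20).

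**What is measured again.** Of the HHIA, section 5.1 says: "It will be administered at the beginning and end of Part 1 to document baseline handicap status prior implementing Part 2 of the study". The SSQ is handled the same way. At Part 2 entry the participants complete the HHIA, the SSQ and the unaided APHAB. For the delayed-treatment group, "At 6 months post-entry their pure tone hearing thresholds will be measured to determine possible changes in hearing sensitivity". Neither the PCL-M nor any other PTSD measure is listed at Part 2 entry, week 1, months 1, 2, 4 or 6, or any delayed-group visit.

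**Other PTSD information.** The Part 1 case history asks about PTSD. From the patient record, "behavioral health diagnosis and treatment history also will be collected from the VA Computerized Patient Record System (CPRS) to confirm status". This too is a Part 1 item, and no update is described.

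**What happens in between.** Most participants are expected to need 4 to 5 Part 1 sessions, with 4 more allowed. Section 5.2 lets people be called later as replacements and sets no maximum wait. Section 5.7 says: "Participants with PTSD will be referred to their local VA for behavioral health services if they are not receiving services currently".

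**How PTSD enters the analysis.** Question d in section 3.0 concerns hearing aids that give "mild high-frequency gain and does PTSD influence benefit". In section 5.6 PTSD enters the Part 2 analyses through group membership. Covariates may be added to the longitudinal models, but no PTSD score or PTSD treatment variable is named.

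**The concern.** PTSD is the moderator in questions d and e, and section 3.0 expects it to restrict perceived benefit. PTSD symptoms can change. The background in section 2.0 says that treating PTSD and depression symptoms might improve recovery, and section 5.7 sends untreated participants towards such care. The plan rechecks another group-defining score (HHIA) and the delayed group's hearing thresholds, but not PTSD.

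If some participants cross the cut between screening and fitting, and if benefit depends on symptoms while the aids are worn, the comparison of mTBI-only with mTBI+PTSD is diluted towards zero. A null answer to question d could then mean either that PTSD does not matter or that the labels had drifted. No data would be available to tell these apart, and the missing scores could not be recovered later.

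**Working it through.** **The plan's nearest figure.** No figure is given for the PTSD contrast. The nearest is the Part 2 four-group ANOVA in section 5.6 (100 participants, alpha 0.01, power 0.80, detectable effect size 0.38). With a noncentral F on 3 and 96 degrees of freedom and noncentrality 0.38² × 100 = 14.44, power is 72.9%; 80% needs an effect size of 0.405. That mismatch is a separate matter, and nothing below depends on it.

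**Age of the label.** Let g be the time from screening to Part 2 entry, for which no limit is stated.

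| | At fitting | At final visit |
|---|---|---|
| Immediate treatment | g | g + 6 months |
| Delayed treatment | g + 6 months | g + 12 months |

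**Dilution.** Let p be the share of mTBI+PTSD now below the cut and q the share of mTBI-only now above it. Suppose mean benefit is m1 for anyone currently above the cut and m0 for anyone below it. Then:

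- labelled mTBI+PTSD: (1 − p)·m1 + p·m0
- labelled mTBI-only: (1 − q)·m0 + q·m1
- difference: (1 − p − q)·(m1 − m0)

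For the same power at the same standard deviation, the sample size rises by 1/(1 − p − q)².

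**Numbers.** The documents give neither p nor q, so all values are assumed. Power is for a two-sample t test with 25 per group (section 5.6). The true contrast is set so that a current label gives 80% power: 1.00 SD at alpha 0.01 and 0.81 SD at alpha 0.05.

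| p | q | Contrast kept | Sample-size multiplier | Power, alpha 0.01 | Power, alpha 0.05 |
|---|---|---|---|---|---|
| 0 | 0 | 100% | 1.00 | 80% | 80% |
| 0.1 | 0 | 90% | 1/0.90² = 1.23 | 69% | 71% |
| 0.2 | 0 | 80% | 1/0.80² = 1.56 | 56% | 61% |
| 0.2 | 0.1 | 70% | 1/0.70² = 2.04 | 43% | 50% |
| 0.3 | 0.1 | 60% | 1/0.60² = 2.78 | 30% | 39% |

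Referral to care can act only on p. A non-zero q needs another cause, such as symptoms that emerge later or scores that sit close to the cut. Table 1 leaves no gap at the cut, so a change from 20 to 21 switches the label.

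**The delayed groups.** Section 5.1 draws the delayed-treatment group from mTBI-only. Section 5.2 describes an mTBI-only and an mTBI+PTSD delayed group, and section 5.6 counts four groups of 25. Under section 5.1 nobody labelled with PTSD waits the extra 6 months. Under section 5.2, 25 participants do. The two passages must be reconciled before anything can be said about differential label age.

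**The case against.** The strongest reply is that PTSD at enrolment is a legitimate subgroup. It is fixed before treatment, it is common to all groups, and it answers a useful question: does a veteran who presents with PTSD benefit? This stands, and it is why the screening group should remain the main subgroup. The limit is on interpretation: the label cannot be read as PTSD present during hearing aid use.

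Two further replies carry weight. Part 2 is secondary, and section 5.2 calls it preliminary. The label also has some support beyond one score, from the case history and the patient record. Both reduce the weight of the point, but neither source updates status after Part 1.

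A reader might also infer more than the documents support:

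- *The label is out of date.* No rate of change, referral timing or referral uptake is given. The referral covers only people not already in services, and recruitment includes behavioral health clinics, so some may already be in care. Its place under withdrawal also leaves its reach unclear.
- *The error is worse in the delayed arm and contaminates a pooled PTSD effect.* The first half depends on the conflict between sections 5.1 and 5.2. The second describes an analysis that the plan does not contain: section 5.6 compares groups and does not pool PTSD across immediate and delayed treatment. Within either arm, both PTSD groups would follow the same schedule.
- *The PCL-M taken just before fitting should replace the screening label.* In the delayed groups that score comes 6 months after entry. It would be a post-assignment variable, defined differently by arm.

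**Conclusion.** The point holds in a limited form. PTSD is scored once, at Part 1 screening. The gap to Part 2 has no stated limit, and no Part 2 visit repeats the score. The label may therefore be stale at fitting, and the data to check this would not exist.

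The size is unknown. Over the assumed range the PTSD contrast keeps between 90% and 60% of its value, a sample-size multiplier of 1.23 to 2.78. This rests on assumed p and q and on benefit depending only on which side of the cut a participant is on at fitting. If benefit depends partly on the earlier status, the loss is smaller; if nobody crosses the cut, it is nil. Whether the extra 6 months before delayed fitting affects any PTSD-labelled group cannot be settled until sections 5.1 and 5.2 agree. This is an inexpensive improvement to a secondary question and does not invalidate Part 2.

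**What to change.** 1. Add the PCL-M at Part 2 entry in every Part 2 group, alongside the HHIA, SSQ and APHAB already given there.
2. Keep the screening group as the assignment stratum and the main subgroup. Prespecify an analysis of benefit with the Part 2 entry PCL-M score as moderator, used as a score so that small moves around the cut do not switch categories.
3. Repeat the PCL-M at month 6 in the delayed groups, before fitting, and at the final visit in all groups. Use these values for description or sensitivity analysis only, because they are post-assignment.
4. Reconcile sections 5.1 and 5.2 on who forms the delayed-treatment groups.

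The cost is a few minutes per participant at each of two or three existing visits and a small amendment. The instrument is already in use, and no new visit is needed.

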6.0 Reporting

The occurrence of Serious Adverse Events, Unanticipated Problems and Protocol Deviations will be reported to the local lead investigator via telephone, encrypted VA email, or in person with documentation submitted to the project PI through encrypted VA email or in person. A report will be developed by the local lead investigator and submitted to the VA Central IRB through its secure SharePoint site, and as required to the local site R&D Committee.

7.0 Privacy and Confidentiality

Protected Health Information will be collected during the course of this study but not disclosed outside of approved study investigators and staff. The following include the steps that will be taken to ensure participant privacy and confidentiality.

- All paper records with identifiable information will be retained at each site in a locked cabinet within a secure laboratory space.
- All coded paper records will be retained at each site in a locked cabinet in a secure laboratory space and kept separate from all identifiable information.
- The study PI and each site will retain linkage code documentation that is kept secure and separate from data and other identifiable information.
- Only information related to the study will be requested and obtained.

- Only investigators and study staff will have access to identifiable participant information and data.
- The laboratory desktop computers with custom and non-VA software used for data acquisition will be password protected and disconnected from the internet and VA intranet. Laboratory desktop computers connected to the VA intranet will be used for administration of questionnaires and data entry into REDCap. We will use the VA-approved version of REDCap within the VA Informatics and Computing Infrastructure system (VINCI). The VINCI system also will be used for data storage and analysis. Laboratory laptops will be encrypted per VA guidelines, password protected and blocked from internet use.
- Coded raw data residing on the laboratory computers will be copied onto storage drives for backup at each site. These drives will be in physically locked and secured laboratory spaces. They will be encrypted to FIPS 140-2 standards and approved by the site ISOs prior to purchase and use. It should be noted that the PI currently uses this type of backup system in her laboratory.
- Some data will be transferred to the drive allocated to the study PI on the VAPHS research server (currently is the “L:\Hearing_Lab”). However, most of the raw data acquired from this study will be acquired and stored in the VA-approved version of REDCap with the VINCI system or directly inputted into VINCI for storage. These data will be coded with access limited to study investigators and staff.
- No identifiable data will be included in presentations and publications.
- Interviews and private study related conversations will be conducted in private rooms.
- After participants have provided informed consent to participate in the study, contact relating to scheduling, session reminders, and participant questions about non-sensitive information will be allowed by e-mail and telephone text if preferred by the individual participants. No sensitive information will be transmitted my e-mail or text.

8.0 Communication Plan

The PI and lead investigators will have conference calls at least twice per month to maintain coordination of the study activities and to address any issues. Once a year, the PI will meet face-to-face with Drs. [name] and [name] and their respective study teams to check procedural fidelity and data integrity. Additional meetings will be scheduled as needed.

Data monitoring will occur monthly by the lead investigator at each sites with monthly reports submitted to the PI for review and signature. The participant safety and data accrual, security, and fidelity will be reviewed by site and in aggregate. In addition, all three teams will complete yearly internal audits to confirm the fidelity of their procedures and documentation, and to insure appropriate data quality and security. The results of these audits also will be reviewed by the PI with corrective actions taken and reported as needed. The data accrual is expected to be 50% at the Pittsburgh site, 25% at the PVAMC site and 25% at the VASFHS/University of South Dakota site. If more than 5%

of participants per year per site have protocol deviations, the study personnel at that site will receive re-training. The lead investigators at each site will receive copies of the documents approved by the Central IRB for the study, and the documents required for submission at the local site.

To ensure that all regulatory and IRB requirements have been met at each site prior to implementing the study procedures, the lead investigators at each site will submit a copy of the local IRB application, consent forms, HIPAA documents and approval letters to the PI.

Copies of all Central and local IRB documents will be retained in regulatory binders by the PI and the lead investigators at each site will retain copies of the Central IRB documents transmitted to them, as well as their local IRB documents.

Serious Adverse Events and Unanticipated Problems will be reported to the lead investigator at each site who will contact the PI. Documentation will be submitted to the Central IRB by the lead investigator with copies submitted to the PI. Copies of the reports will be retained by the PI and the lead investigator at their site. The PI also will submit interim results that may impact conduct of the study.

All sites will continue to collect data until the full complement of participants has completed the study or until the study has been concluded.

